Subjects who receive topical rescue therapy only may continue to receive investigational product provided no discontinuation criteria (Section 4.1.6) are met. Investigational product will be immediately discontinued in subjects who receive systemic rescue therapy, which is a prohibited medication (Section 4.7.3). All subjects should complete the schedule of study visits and assessments whether or not they continue treatment with investigational product, and whether or not they receive systemic rescue therapy. Investigators should make every attempt to conduct efficacy and safety assessments immediately before administration of any systemic rescue therapy. If it is not possible for the subject to complete the remaining visits, then the subject should complete the early discontinuation visit as outlined in the schedule of study procedures (Table 8).

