3.4.2.2 Handling of Dropouts and Missing Data

If any component of SCORAD, 5-D Pruritus Score, POEM, DLQI or EASI score is missing, the calculation of the score will be set to missing.

For the analysis of efficacy responder endpoints, including the proportion of subjects achieving both IGA score of 0 (clear) or 1 (almost clear) and a reduction from baseline of ≥ 2 points, EASI 50, EASI 75, EASI 90 and peak pruritus NRS responders, subjects who discontinue investigational product, withdraw from the study, or require rescue therapy will be considered as non-responders. For the EASI 75 and IGA endpoints, additional sensitivity analyses will be performed using the last non-missing post-baseline value carried forward approach to assess the impact of including efficacy data beyond the use of rescue therapies. For subjects who receive rescue therapies, the last response value recorded on the day of, or prior to, the subject received a prohibited rescue therapy will be carried forward.

The continuous efficacy endpoints, including, percent change from baseline to Week 16 in SCORAD, change from baseline to Week 16 in peak pruritus NRS, skin pain NRS, 5-D pruritus (itch) score, percentage of BSA affected by AD, POEM, and DLQI will be analyzed using MMRM. All data points for subjects in the ITT population will be included in the analysis, up to and including the day the rescue therapy is used.

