3.4.2.3 Secondary Efficacy Analyses

IGA Score 0 or 1 with ≥ 2 Grade Reduction from Baseline to Week 16

The percentage of subjects achieving an IGA score of 0 (clear) or 1 (almost clear) and a reduction from baseline of ≥ 2 points at Week 16 will be analyzed using a logistic regression model including treatment group, randomization stratum (total serum IgE level < 150 kU/L or ≥ 150 kU/L), and baseline IGA as categorical factors. The coefficient of the treatment effects at Week 16 obtained from the logistic regression will then be used in an MCP-Mod analysis with 4 candidate models for the dose response (linear, E_{\max} , and 2 Hill- E_{\max} models). Details of the candidate models are provided in [Appendix 1](#). As part of the MCP-Mod model, the testing of the 4 candidate dose response models will be adjusted for multiplicity using a family-wise error rate of 0.10. If more than 1 candidate model shows a statistically significant dose response, the final model will be selected based on the Akaike Information Criteria obtained from each model.

The composite estimand of primary interest is the difference in IGA response rate at Week 16 between MEDI3506 and placebo in the ITT population. Subjects who withdraw from the study or require rescue therapy will be considered as non-responders. From the final model obtained

from the MCP-Mod dose response analysis, the difference in IGA response rate between the placebo and each MEDI3506 group will be estimated along with the 90% CI. For each MEDI3506 group versus placebo, the results will be presented as the difference in response rates, the 90% CI for the difference in response rates, and two-sided p-value.

A plot showing the percentage of subjects achieving IGA response in each treatment group by visit will be provided. In addition, barplot of IGA response rate at Week 16 in each treatment group will be provided.

Supplementary analyses will be performed to assess the sensitivity of the assumptions of the statistical methods used in the primary analysis for the IGA endpoint.

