A logistic regression model of IGA response rate at Week 16 will be performed based on the ITT population. The model will include treatment group and randomization stratum (total serum IgE level < 150 kU/L or ≥ 150 kU/L) as categorical factors, and baseline IGA score as a covariate. Subjects who discontinue investigational product, withdraw from the study, or require rescue therapy will be considered as non-responders. For each MEDI3506 group compared with placebo, differences in response rates, 90% CIs for the differences in response rates (Ge et al, 2011), and two-sided p-values will be reported. If the number of responders is < 5 in any MEDI3506 group, the logistic regression model will not be used. Instead, the 90% CI and p-value for the difference in response rates will be calculated using an unconditional exact method (Chan and Zhang, 1999).

An analysis based on the ITT population will be done using all available data from subjects irrespective of whether or not they completed treatment, including data from subjects who received rescue therapy. Subjects who discontinue investigational product or withdraw from the study before Week 16 will be considered as non-responders. The analysis will be performed using the same MCP-Mod as described for as described above for the secondary efficacy analysis for IGA. In addition, a logistic regression analysis similar to that described above, will also be performed for this ITT population for all observed cases.

Another supplementary analysis will be performed using the ITT population in which data from assessments performed after rescue therapies are received are excluded and a last observation carried forward approach applied for missing data. The logistic regression and MCP-Mod dose response model used for this analysis and the presentation of results will be similar as described above for the secondary efficacy analysis for IGA. In addition, a logistic regression analysis like that described above, will also be performed for this ITT population with LOCF.

Another supplementary analysis will be performed using the ITT population excluding data from subjects CCI whose treatment allocations were accidentally unblinded at the site. The analysis will be performed using the same MCP-Mod as described above for the secondary efficacy analysis for IGA.

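### The supplementary IGA analysis said to use all available data scores everyone who stops product before Week 16 as a non-responder, so post-rescue data enter only for subjects still on product

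*SAP*

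**What the plan says.** **Supplementary analysis (SAP 3.4.2.3; same rule in Protocol 4.8.3.3).** The scope is an ITT analysis "using all available data from subjects irrespective of whether or not they completed treatment, including data from subjects who received rescue therapy". The scoring rule follows at once: "Subjects who discontinue investigational product or withdraw from the study before Week 16 will be considered as non-responders". The SAP adds a logistic regression for all observed cases and does not say whether the scoring rule applies to it.

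**Main IGA analysis.** The IGA text in SAP 3.4.2.3 and Protocol 4.8.3.3 says: "Subjects who withdraw from the study or require rescue therapy will be considered as non-responders". Stopping product is not listed. SAP 3.4.2.2 covers the responder endpoints, names IGA among them, and says: "subjects who discontinue investigational product, withdraw from the study, or require rescue therapy will be considered as non-responders".

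**Follow-up and rescue.** Protocol 4.7.4 says: "All subjects should complete the schedule of study visits and assessments whether or not they continue treatment with investigational product". It separates two routes. For topical rescue: "Subjects who receive topical rescue therapy only may continue to receive investigational product provided no discontinuation criteria (Section 4.1.6) are met". For systemic rescue: "Investigational product will be immediately discontinued in subjects who receive systemic rescue therapy". SAP 3.3.6 makes no such split. It says a subject given prohibited or rescue therapy for atopic dermatitis that may affect efficacy assessments should stop product.

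**Carried-forward analysis.** SAP 3.4.2.2 plans a last-observation-carried-forward analysis of EASI 75 and IGA "to assess the impact of including efficacy data beyond the use of rescue therapies". For rescued subjects it then carries forward the last value recorded on or before the day of rescue.

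**The concern.** The protocol asks sites to keep assessing subjects after they stop product or receive rescue. An analysis announced as using all available data regardless of treatment completion is the natural place to use those visits. As written, it replaces the observed IGA of every subject who stopped product with non-response. The corresponding EASI supplementary analysis (SAP 3.4.1.4) uses the same all-available-data language with no override, so two analyses described alike answer different questions.

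The practical risk is in interpretation. Under one reading of the main rule, moving from the main to the supplementary analysis adds some post-rescue data and removes off-product data. If the two results agree, that could be reported as robustness when two changes have cancelled.

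**Working it through.** No stated figure depends on this rule, so there is nothing to reproduce. The check is a comparison of rules, followed by an illustration.

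**Step 1. Apply each rule to each pattern of events before Week 16** (NR = scored non-responder; observed = Week 16 IGA used; rescue and product as in Protocol 4.7.4).

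| Pattern | Main, SAP 3.4.2.3 and Protocol 4.8.3.3 | Main, SAP 3.4.2.2 | Supplementary as written |
|---|---|---|---|
| On product, no rescue | observed | observed | observed |
| On product, topical rescue | NR | NR | observed |
| Off product, no rescue | observed | NR | NR |
| Off product, rescue | NR | NR | NR |
| Withdrawn | NR | NR | NR |

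- The supplementary column overrides both off-product rows. That contradicts its stated scope.
- Post-rescue data enter in one row only: rescued and still on product.
- Against the first main rule, rows two and three both change, in opposite directions. Against the second, only row two changes, and off-product data are absent from both analyses.
- If SAP 3.3.6 were applied so that every rescued subject stopped product, row two would be empty and no post-rescue data would enter.

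**Step 2. Illustrate the size.** From SAP Appendix 1: response rates of 10% on placebo and 30% at maximum effect, a difference of 20 points. Assumed, with no source in the documents: 5% withdrawn; 5% off product with rescue; a share *q* off product without rescue (0 to 15%); a share *t* on product with topical rescue (0 to 20%); equal shares in both arms; every observed group responding at its arm's rate.

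Difference in response rate, in points:
- Main, SAP 3.4.2.3: 20 × (1 − 0.10 − *t*)
- Main, SAP 3.4.2.2: 20 × (1 − 0.10 − *q* − *t*)
- Supplementary as written: 20 × (1 − 0.10 − *q*)

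| *q* | *t* | Main, 3.4.2.3 | Main, 3.4.2.2 | Supplementary |
|---|---|---|---|---|
| 10% | 10% | 16.0 | 14.0 | 16.0 |
| 0% | 20% | 14.0 | 14.0 | 18.0 |
| 10% | 0% | 18.0 | 16.0 | 16.0 |
| 15% | 0% | 18.0 | 15.0 | 15.0 |

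The gap from the first main rule is 20 × (*t* − *q*), which runs from −3 to +4 points. In the first row it is zero, although 20% of each arm is handled differently. The gap from the second main rule is 20 × *t*, 0 to 4 points, and comes from on-product rescue data alone.

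**Step 3. Illustrate the proposed rule.** If only the withdrawn 5% lack a Week 16 value, the difference is 20 × 0.95 = 19.0 points. In the first row that is 3 points above the 16.0 of the rule as written: 20 × 0.10 = 2 from unrescued stoppers and 20 × 0.05 = 1 from rescued stoppers. The direction depends on the equal-response assumption. If rescued placebo subjects respond well, the difference would shrink.

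**The case against.** One could read the scope sentence as saying only that all subjects stay in the denominator, with stoppers scored as failures. That is a coherent composite analysis, but it does not use all available data, and the matching EASI analysis, described in the same way, has no override. The conflict remains.

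Three stronger readings are tempting, and the documents do not support them.

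- *That the analysis cannot show any effect of post-rescue data.* Under Protocol 4.7.4 rescue starts with topical therapy and those subjects may stay on product, so their observed scores do enter. The stronger claim needs SAP 3.3.6 to override Protocol 4.7.4, and the documents do not settle that. Nor do they give figures to say that most post-rescue or off-product visits are lost.
- *That it discards data the main IGA analysis keeps.* This holds under the IGA text of SAP 3.4.2.3 and Protocol 4.8.3.3, but not under SAP 3.4.2.2. The first reading has good support, because both documents add product discontinuation for EASI 50, 75 and 90 and omit it for IGA. The contradiction still stands.
- *That a difference from the main analysis could never be attributed.* SAP 3.4.2.3 also plans a logistic regression scoring discontinuation, withdrawal and rescue as non-response. If the override applies to the all-observed-cases regression, those two differ by the rescue rule alone. If it does not apply, that regression already uses off-product data. The SAP does not say which.

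The repeated-measures GEE model in the same section states no exclusion of its own, so this may not be the only IGA analysis using off-product visits.

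The size argument largely stands. The shares are assumptions, and one subject in a 58-subject arm is 1.7 points. With 58 per arm the unadjusted 90% half-width is 1.645 × √[(0.30 × 0.70 + 0.10 × 0.90)/58] = 11.8 points.

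**Conclusion.** The rule is wrong as written: followed literally, it does not deliver the analysis that the same paragraph describes. This rests on the text alone and needs no assumption about event rates.

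What is lost is the observed Week 16 IGA of subjects off product, including those who stopped because of systemic rescue. How rescue or stopping after the last planned dose at Week 12 (SAP 2.2) should be counted is also unclear. Whether the comparison with the main analysis mixes two changes depends on which main rule governs, and the SAP states both.

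The numerical effect is modest, 0 to about 4 points under the assumed shares, and could be zero through cancellation. It concerns one supplementary analysis of a secondary endpoint. The primary EASI result and the main IGA estimand are unaffected by the override, although the conflict over the main IGA rule needs settling in its own right.

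The carried-forward analysis in SAP 3.4.2.2 is a separate, smaller fault. Its stated purpose is to include data beyond rescue, and its method excludes them.

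**What to change.** 1. In SAP 3.4.2.3 and Protocol 4.8.3.3, remove product discontinuation from this supplementary rule. Use the observed Week 16 IGA whether or not product was stopped or rescue given, and score as non-responders only subjects with no Week 16 value. This also covers a missed Week 16 visit without withdrawal, which the current rule does not address.
2. State that the accompanying all-observed-cases logistic regression follows the same rule.
3. Reconcile SAP 3.4.2.2 with the IGA text of SAP 3.4.2.3 and Protocol 4.8.3.3 on whether stopping product is non-response in the main IGA analysis.
4. Reconcile SAP 3.3.6 with Protocol 4.7.4 on product discontinuation after rescue. This review takes no position on which should stand.
5. In SAP 3.4.2.2, reword the purpose of the carried-forward analysis to say that it excludes post-rescue data.

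An all-data analysis of EASI 75 is optional, since SAP 3.4.2.3 plans no such supplement for that endpoint.

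The cost is a few clauses in the SAP and one in the protocol, with no new data collection. The revised estimate may look less favourable if rescued placebo subjects respond, but showing that is part of the purpose of such an analysis.

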3.4.2.4 Subgroup Analyses

The consistency of the detected overall treatment effect on the IGA response at Week 16 will be assessed in a subgroup of subjects. A logistic regression model including treatment group, randomization stratum (total serum IgE level < 150 kU/L or ≥ 150 kU/L), and baseline IGA as categorical factors, will be used in a similar way as described in Section 3.4.2.3 for the following subgroup populations of interest:

- Total serum IgE level (< 150 kU/L vs ≥ 150 kU/L).
- IGA score (3 vs 4).
- Baseline EASI (≤ 25 points vs > 25 points).
- *S aureus* in lesional skin ($<$ median vs \geq median) (at final analysis only).
- *S aureus* in non-lesional skin ($<$ median vs \geq median) (at final analysis only).
- Age (18 to 35 years of age vs 36 to 75 years of age).
- Age at onset of AD (< 18 years of age vs ≥ 18 years of age).
- Parent having a history of AD (presence vs absence).
- Sex (male vs female).
- Race (White vs non-White).
- Region (North America vs Europe/Australia).
- Blood eosinophil count (< 300 cells/ μ L vs ≥ 300 cells/ μ L).
- Aeroallergens (presence vs absence).
- Food allergies (presence vs absence).
- Contact allergies (presence vs absence).
- Asthma comorbidity (presence vs absence).

The logistic regression will be fitted separately to each subgroup. The analysis for each subgroup will be performed if the subgroup has at least 20% of subjects in the ITT population.

Similarly, the consistency of the detected overall treatment effect on the percentage of subjects achieving EASI 75 at Week 16 will be assessed in subgroup of subjects described above using a similar logistic regression model as described previously (Section 3.4.2.3).

3.4.3 Other Efficacy Analyses

Descriptions of the exploratory efficacy endpoints are provided (Section 3.4.2.1), except for SNOT-22 and ACQ-6, provided below.

The SNOT-22 is a validated questionnaire for assessing the impact of chronic rhinosinusitis on quality of life. The SNOT-22 contains a list of 22 symptoms and social/emotional consequences of a patient's nasal disorder, and measures how severe each symptom is and the social/emotional consequences of symptoms over a 2-week period on a scale from 0 (no problem) to 5 (problem as bad as it can be). A total score is summed.

The ACQ-6 is a questionnaire developed and validated to measure asthma control. The ACQ includes 6 questions regarding symptoms at night, in the morning, limitation of normal daily activities, dyspnea, wheezing, and beta-2 agonist use. Subjects are asked to recall how their asthma has been during the previous week and to answer questions using a 7-point scale with 0 = no impairment and 6 = maximum impairment). ACQ-6 does not include spirometry and is the equally weighted mean of 6 questions.

3.4.3.1 Number and percentage of subjects achieving EASI 90, EASI 75, and EASI 50, at Weeks 2, 4, 8, 12, 16, 20, and 24

The number and percentage of subjects achieving EASI 90, EASI 75, and EASI 50 by Weeks 2, 4, 8, 12, 16, 20, and 24 will be summarized by visit separately for each endpoint. Analyses using a GEE model for repeated measures will be performed separately for each endpoint and will include all data up to Week 24. Details of the model are similar to those described for the additional analysis of the IGA response at Week 16 (Section 3.4.2.3).

3.4.3.2 Percentage change from baseline to Weeks 2, 4, 8, 12, 16, 20, and 24 in EASI score

The percent change from baseline to Weeks 2, 4, 8, 12, 16, 20, and 24 in EASI score will be summarized descriptively by visit and analyzed using a MMRM including data from visits up to Week 24 in a similar way as described for percent change from baseline to Week 16 in EASI score (Section 3.4.1.3).

3.4.3.3 Percentage of subjects achieving IGA 0/1 and ≥ 2 grade reduction from baseline at Weeks 2, 4, 8, 12, 16, 20, and 24

The number and percentage of subjects achieving an IGA response at Weeks 2, 4, 8, 12, 16, 20, and 24 will be summarized by visit, and analyzed using the GEE model as described for IGA response at Week 16 (Section 3.4.2.3).

3.4.3.4 Change from baseline to Weeks 2, 4, 8, 12, 16, 20, and 24 in %BSA affected by AD

Change from baseline to Weeks 2, 4, 8, 12, 16, 20, and 24 in percent BSA affected by AD will be summarized descriptively by visit, and analyzed using a MMRM as described for percent change from baseline to Week 16 in EASI score (Section 3.4.1.3).

3.4.3.5 Peak pruritus NRS: reduction of ≥ 3 from baseline to Weeks 2, 4, 8, 12, 16, 20, and 24

The number and percentage of subjects achieving reduction of ≥ 3 from baseline to Weeks 2, 4, 8, 12, 20, and 24 in weekly mean of daily peak pruritus NRS will be summarized by visit and analyzed using the GEE model as described above for IGA response at Week 16 (Section 3.4.2.3).

3.4.3.6 Peak pruritus NRS: reduction of ≥ 4 from baseline to Weeks 2, 4, 8, 12, 16, 20, and 24

The number and percentage of subjects achieving reduction of ≥ 4 from baseline to Weeks 2, 4, 8, 12, 16, 20, and 24 in weekly mean of daily peak pruritus NRS will be summarized by visit and analyzed using the GEE model as described above for IGA response at Week 16 (Section 3.4.2.3).

3.4.3.7 Peak pruritus NRS: change from baseline to Weeks 2, 4, 8, 12, 16, 20, and 24

Change from baseline to Weeks 2, 4, 8, 12, 16, 20, and 24 in the weekly mean of daily peak pruritus NRS will be summarized descriptively by visit and analyzed using a MMRM as described for percent change from baseline to Week 16 in EASI score (Section 3.4.2.3)

3.4.3.8 Skin pain NRS: change from baseline to Weeks 2, 4, 8, 12, 16, 20, and 24

Change from baseline to Weeks 2, 4, 8, 12, 16, 20, and 24 in the weekly mean of daily peak skin pain NRS will be summarized by visit and analyzed using a MMRM as described for percent change from baseline to Week 16 in EASI score (Section 3.4.2.3).

3.4.3.9 SCORAD: Percent change from baseline to Weeks 2, 4, 8, 12, 16, 20 and 24

Percent change from baseline to Weeks 2, 4, 8, 12, 16, 20, and 24 in SCORAD will be summarized descriptively by visit and analyzed using a MMRM as described for the percent change from baseline to Week 16 in EASI score (Section 3.4.2.3).

3.4.3.10 PGI-S at Weeks 2, 4, 8, 12, 16, 20 and 24

PGI-S at Weeks 2, 4, 8, 12, 16, 20, and 24 will be summarized by visit with descriptive statistics including number of subjects, mean, SD, median, minimum, and maximum. In addition, the number and percentage of subjects in each category will also be summarized by visit.

3.4.3.11 Change from baseline to Weeks 2, 4, 8, 12, 16, 20, and 24 in 5-D itch

Change from baseline to Weeks 2, 4, 8, 12, 16, 20, and 24 in 5-D itch will be summarized by visit and analyzed using a MMRM as described for percent change from baseline to Week 16 in EASI score (Section 3.4.2.3).

3.4.3.12 Change from baseline to Weeks 2, 4, 8, 12, 16, 20, and 24 in POEM

Change from baseline to Weeks 2, 4, 8, 12, 16, 20, and 24 in POEM will be summarized by visit and analyzed using a MMRM as described for percent change from baseline to Week 16 in EASI score (Section 3.4.2.3).

3.4.3.13 Change from baseline to Weeks 2, 4, 8, 12, 16, 20, and 24 in DLQI

Change from baseline to Weeks 2, 4, 8, 12, 16, 20, and 24 in DLQI will be summarized by visit and analyzed using a MMRM as described for percent change from baseline to Week 16 in EASI score (Section 3.4.2.3).

3.4.3.14 Change from baseline to Weeks 16 and 24 in SNOT-22

Change from baseline to Week 16 and to Week 24 in SNOT-22 will be summarized separately by treatment group using descriptive statistics including number of subjects, mean, median, SD, minimum, and maximum.

